### **3.3 Discontinuation from Study Treatment**

Patients may be withdrawn from study treatment for any of the following reasons:

- Disease progression (PD) based on RECIST Version 1.1 criteria, where the patient is no longer receiving benefit in the opinion of the treating Investigator.
  - However, patients who are receiving benefit in the opinion of the treating Investigator may be allowed to stay on study on a case-by-case basis with agreement from the Medical Monitor and if the patient re-consents to continue receiving the study drug and meet the criteria listed in Section 5.2.

Clinical progression (definitive clinical signs of PD), but a recent radiographic assessment did not meet the criteria for PD according to RECIST Version 1.1

- Adverse event
- Death
- Pregnancy
- Withdrawal of consent by patient
- Lost to follow-up
- Physician decision
- Study terminated by Sponsor
- Other

After discontinuation from protocol treatment, patients must be followed for AEs for at least 30 days after their last dose of study drug. All new AEs occurring during this period must be reported and followed until resolution, unless, in the opinion of the Investigator, these values are

*CONFIDENTIAL*

not likely to improve because of the underlying disease. In this case, the Investigator must record his or her reasoning for this decision in the patient's medical records and indicate on the AE pages that the outcome is not resolved on the electronic case report form (eCRF).

All patients who have Grade 3 or 4 laboratory abnormalities (per National Cancer Institute Common Terminology Criteria for Adverse Events [NCI CTCAE Version 5.0]) at the time of discontinuation must be followed until the laboratory values have returned to Grade 1 or 2, unless it is, in the opinion of the Investigator, not likely that these values are to improve. In this case, the Investigator must record his or her reasoning for making this decision in the patient's medical records and indicate on the AE pages that the outcome is not resolved on the eCRF.

#### **4. STUDY REGISTRATION**

The patient must willingly consent after being informed of the procedures to be followed, the experimental nature of the treatment, potential benefits, alternatives, side-effects, risks, and discomforts. Human protection committee (IRB/IEC) approval of this protocol and any associated ICFs is required. Eligible patients who wish to participate in the study will be enrolled into the study.

Registration must occur prior to the initiation of study treatment. Patient registration and dose level assignment will be performed by Sarah Cannon Development Innovations (Innovations). The study site will document the patient identification number, dose level, and date of enrollment on the Patient Enrollment Form.

For additional information regarding study registration, please refer to the Study Reference Manual.

#### **5. STUDY DESIGN**

This study is a Phase I, two-part, multicenter, open-label, multiple-dose, first-in-human study of the antibody-drug conjugate, DS-6157a, given as a single agent to patients with GIST. Patients will be enrolled in this study in the United States (US), Japan, and other country(ies).

In Dose Escalation (Part 1), approximately 40 patients may be enrolled. Once the MTD and RDE are established for DS-6157a in Part 1, enrollment in Dose Expansion (Part 2) will commence in two cohorts. Up to approximately 30 patients with GIST who have been previously treated with IM and at least one other post-IM treatment will be enrolled in Cohort 1, and up to approximately 30 patients with GIST who progressed on IM or who are intolerant to IM but have not received post-IM treatment (2nd line) will be enrolled in Cohort 2. Enrollment into Dose Escalation will not be restricted to patients with evidence of GPR20 expression. Patient selection may be considered for Part 2 based on the biomarker assessments and its correlation with safety/efficacy signals in Part 1.

Based on all available data collected in Dose Escalation (e.g., PK, safety, efficacy, and biomarker data), multiple doses or regimens less than or at the MTD (if attained, or the highest dose evaluated) may be selected as RDEs for further evaluation in Dose Expansion. If this is the

[figure not shown]
*CONFIDENTIAL*

case, up to approximately 30 patients may be randomized into each dose or regimen in one or more cohorts during Dose Expansion.

DS-6157a will be administered intravenously (IV) on Day 1 of each cycle on a 21-day schedule. The study will identify an MTD (see Section 5.1.3) and an RDE (see Section 5.1.4) for DS-6157a.

The study schema is presented in Figure 1.

**Figure 1 Study Schema**

GIST: gastrointestinal stromal tumors, RDE: recommended dose for expansion

\*These are provisional doses. Actual dose levels will be determined by clinical toxicity findings in each dose cohort and the Bayesian logistic regression model (BLRM). Higher or intermediate doses may also be considered.

\*\*DS-6157a dose will be determined in Dose Escalation (Part 1).

\*\*\*Cohort 1 includes patients who have been previously treated with imatinib and at least one post-imatinib treatment.

#Cohort 2 will be initiated after acceptable efficacy is demonstrated objective responses or SD for a minimum of 6 months in  $\geq 20\%$  of 10 or more patients treated with DS-6157a at RDE) in Dose Escalation and Dose Expansion Cohort 1.

CONFIDENTIAL

## 5.1 Treatment Plan

DS-6157a will be prepared and administered via intravenous (IV) infusion according to the details in the Pharmacy Manual.

For Dose Escalation (Part 1), on Cycle 1 Day 1 DS-6157a will be infused for  $90 \pm 10$  minutes. A 21-day observation period (Cycle 1) will then occur, at the end of which all relevant safety data will be reviewed. Patients will continue to receive DS-6157a (Q3W) until unacceptable toxicity, progressive disease (PD), death, or withdrawal of consent (Section 3.3). If there is no infusion-related reaction on Cycle 1 Day 1, the subsequent dose of DS-6157a may be infused for  $30 \pm 5$  minutes based on the clinical judgment of the Investigator and/or Medical Monitor, but this reduced infusion rate is not mandatory.

For Dose Expansion (Part 2), on Cycle 1 Day 1 the RDE of DS-6157a will be infused for  $90 \pm 10$  minutes. Patients will then continue to receive DS-6157a (Q3W) until unacceptable toxicity, PD, death, or withdrawal of consent (Section 3.3). If there is no infusion-related reaction after the initial dose, the subsequent dose of DS-6157a may be infused for  $30 \pm 5$  minutes based on the clinical judgment of the Investigator and/or Medical Monitor, but this reduced infusion rate is not mandatory.

For both Dose Escalation and Dose Expansion, the patient's weight at screening (baseline) will be used to calculate the initial dose. The dose will be recalculated if the patient's weight changes by more than 10% from baseline, or per institutional standard even if the weight change is less than  $\pm 10\%$ . This new body weight will be used to calculate the dose for subsequent cycles of DS-6157 infusion.

### 5.1.1 Dose Escalation Procedure

Dose escalation of DS-6157a will be guided by a Bayesian logistic regression model (BLRM) (Neuenschwander et al. 2008) following the escalation with overdose control (EWOC) principle (Babb et al. 1998, Rogatko et al. 2005). The details of the methodology are described in Section 10.7.

Cohorts of 3 to 6 patients will be enrolled and assessed for DLT during Dose Escalation. The first two patients at each dose level in Dose Escalation will start the study treatment (first dose) at least 24 hours apart. Dose escalation decision and enrollment of patients to a new cohort requires completion of DLT evaluation of at least 3 patients treated in the current cohort. Patients who have neither completed the DLT evaluation period with full dose nor experienced a DLT will not be included in the BLRM update. In the event that additional patients in the previous cohort experience a DLT after the enrollment of patients to a new cohort has begun, dose level assignment of the next patient in the study will be based on an updated BLRM using DLT outcome data from all assessed doses thus far, and clinical assessment of the overall safety data by the Sponsor and Investigator(s). The model will also be re-evaluated before enrolment of any additional patients to a cohort if 2 evaluable patients in the cohort experience DLT before the enrollment of the next patient.

CONFIDENTIAL

The next dose level will be chosen by the Sponsor and Investigator(s) based on the dose recommendation by the BLRM as outlined in Section 10.7.3, and clinical assessment of the overall safety data. In addition, any available PK, pharmacodynamics, and efficacy data may be considered for dose escalation decisions. The dose level increase will not be greater than 100% even if the BLRM suggests a dose higher than 100% for next cohort.

The actual number of dose cohorts to be explored in this study will depend on determination of the MTD based on DLTs reported during the DLT evaluation period (Day 1 to Day 21 of Cycle 1 in Dose Escalation). Additional patients may be enrolled at the MTD or any dose levels below the MTD in order to collect sufficient safety and PK data or to characterize safety and PK in specific ethnicities.

For MTD (or RDE if MTD is not observed) determination, the following stopping rules will be implemented for Dose Escalation:

- At least 6 evaluable patients at MTD/RDE level with at least 15 evaluable patients in total enrolled in Dose Escalation, or
- At least 9 evaluable patients have been enrolled at a dose level which is the model's recommendation for the next dose cohort and for which the posterior probability of target DLT rate interval (16%, 33%] is at least 50%, or
- DLT assessment with at least 3 evaluable patients at the maximum tolerated dose level with 95% credible interval for posterior probability of DLT rate is within (5%, 33%), or
- Initial dose level is too toxic.

In order to refine the RDE, additional patients may be enrolled into selected dose levels. These added patients will also be used to generate data on safety, tolerability, PK, potential efficacy, and the correlation with biomarker expression levels. The RDE will be decided based on considerations of the MTD and on an overall assessment of the dose escalation part that will include safety data, efficacy, PK, and biomarker data collected at all doses tested.

**For subjects in Japan only:** Patients in Dose Escalation will be hospitalized during the DLT evaluation period (i.e., Day 1 to Day 21 of Cycle 1 in Dose Escalation). However, temporary stays outside the hospital are permitted at the Investigator's discretion. The Investigator should examine the patient carefully before granting permission for the patient to temporarily leave the clinic. The study site should provide the patient with emergency contact information. Additional safety assessments should be conducted as needed, at the Investigator's discretion.

### 5.1.2 Dose-Limiting Toxicity

Toxicity will be assessed using the NCI [CTCAE Version 5.0](#).

A DLT is defined as any TEAE that occurs during the DLT evaluation period (21 days starting from Cycle 1 Day 1), excluding toxicities clearly related to disease progression or intercurrent illness, that are Grade  $\geq 3$  according to the NCI [CTCAE Version 5.0](#), with the exceptions defined below.

**For Hematologic Toxicities, a DLT is defined as follows:**

*CONFIDENTIAL*

- Grade 4 neutrophil count decreased lasting >7 days
- Grade  $\geq 3$  febrile neutropenia
- Grade  $\geq 3$  anemia requiring transfusion
- Grade 4 anemia
- Grade 4 platelet count decreased, or
- Grade  $\geq 3$  platelet count decreased lasting >7 days
- Grade  $\geq 3$  platelet count decreased associated with clinically significant hemorrhage and/or requiring transfusion
- Grade 4 lymphocyte count decreased lasting  $\geq 14$  days (lymphocyte count decrease of Grade 3 will not be a DLT)

**For Hepatic Organ Toxicities, a DLT is defined as follows:**

- Grade 4 aspartate aminotransferase (AST) or alanine aminotransferase (ALT) increased
- AST or ALT  $> 3 \times$  ULN if accompanied by Grade  $\geq 2$  blood total bilirubin increased with serum alkaline phosphatase  $< 2 \times$  ULN (based on Hy's law definition)
- In patients without liver metastases, AST or ALT  $> 5 \times$  ULN
- In patients with liver metastases, AST or ALT  $> 5 \times$  ULN, if the baseline level was  $\leq 3 \times$  ULN
- In patients with liver metastases, AST or ALT  $> 8 \times$  ULN, if the baseline level was  $> 3 \times$  ULN

**For Non-Hematologic, Non-Hepatic Major Organ Toxicities, a DLT is defined as all TEAEs of Grade  $\geq 3$  with the following exceptions:**

The following AEs will not be considered DLTs:

- Grade 3 fatigue lasting <7 days
- Grade 3 nausea, vomiting, diarrhea, or anorexia that has resolved to Grade  $\leq 2$  within 3 days with maximal medical management
- Grade 3 isolated laboratory findings not associated with signs or symptoms including alkaline phosphatase (ALP) increased, hyperuricemia, serum amylase increased, and lipase increased, and Grade 3 hyponatremia lasting <72 hours developed from Grade 1 at baseline. Symptomatic Grade 4 events will be considered DLTs unless there is documented evidence that the abnormality is associated with disease progression.

For the following non-hematologic, non-hepatic major organ toxicities, a DLT is defined as:

- Symptomatic congestive heart failure

- Any LVEF decline from baseline leading to discontinuation of study treatment
- Grade  $\geq 2$  ILD or pneumonitis
- Grade 3 skin toxicity lasting  $>7$  days or Grade 4 for any duration
- All other Grade  $\geq 3$  non-hematologic, non-hepatic major organ toxicities will be a DLT

If any of the toxicities listed directly above are observed during the DLT evaluation period, the Investigator, Medical Monitor, and Sponsor will discuss if they are to be classified as DLTs.

Premedication (any treatment administered prior to study drug administration to avoid TEAEs), is prohibited during the DLT evaluation period. However, supportive therapy for the treatment of TEAEs is permitted after DS-6157a infusion (e.g., antiemetics are permitted if nausea and vomiting are observed post-dose but will not be administered prior to dosing to prevent nausea and vomiting during the DLT evaluation period).

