Grade 2 ( $>1.5 - 3.0 \times \text{ULN}$ if baseline was normal; $>1.5 - 3.0 \times \text{baseline}$ if baseline was abnormal)	If no documented Gilbert's syndrome or liver metastases at baseline, delay dose until resolved to $\leq$ Grade 1: 
 
- If resolved in <math>\leq 7</math> days from day of onset, maintain dose
 
- If resolved in <math>>7</math> days from day of onset, reduce dose 1 level
 
 If documented Gilbert's syndrome or liver metastases at baseline, continue study treatment
Grade 3 ( $>3.0 - 10.0 \times \text{ULN}$ if baseline was normal; $>3.0 - 10.0 \times \text{baseline}$ if baseline was abnormal)	If no documented Gilbert's syndrome or liver metastases at baseline, repeat testing within 3 days. Delay dose until resolved to $\leq$ Grade 1: 
 
- If resolved in <math>\leq 7</math> days from day of onset, reduce dose 1 level
 
- If resolved in <math>>7</math> days from day of onset, discontinue DS-6157a
 
 If documented Gilbert's syndrome or liver metastases at baseline, repeat testing within 3 days. Delay dose until resolved to $\leq$ Grade 2: 
 
- If resolved in <math>\leq 7</math> days from day of onset, reduce dose 1 level
 
- If resolved in <math>>7</math> days from day of onset, discontinue DS-6157a
 

Grade 4 ( $>10.0 \times \text{ULN}$ if baseline was normal; $>10.0 \times \text{baseline}$ if baseline was abnormal)	Discontinue patient from study treatment
Blood Alkaline Phosphatase Increased	
Grade 3 ( $>5.0 - 20.0 \times \text{ULN}$ if baseline was normal; $>5.0 - 20.0 \times \text{baseline}$ if baseline was abnormal)  or	No modification unless determined by the Investigator to be clinically significant or life-threatening.

CONFIDENTIAL

Grade 4 (>20.0 × ULN if baseline was normal; >20.0 × baseline if baseline was abnormal)	
Gastrointestinal	
Nausea	
Grade 3	Delay dose until resolved to ≤ Grade 1 If resolved in ≤7 days from day of onset, maintain dose If resolved in >7 days from day of onset, reduce dose 1 level
Vomiting	
Grade 3	Delay dose until resolved to ≤ Grade 1 If resolved in ≤7 days from day of onset, maintain dose If resolved in >7 days from day of onset, reduce dose 1 level
Grade 4	Discontinue patient from study treatment
Diarrhea/Colitis	

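### Section 5.1.2 does not clearly say whether Grade ≥3 total bilirubin without a qualifying AST/ALT rise is a DLT: the general rule counts it, the hepatic list omits it

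*Combined protocol and SAP*

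**What the plan says.** Section 5.1.2 has a general rule and three organ groups.

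- **General rule.** Any treatment-emergent event of Grade ≥3 in the 21 days from Cycle 1 Day 1 is a DLT, "with the exceptions defined below". Events clearly due to progression or intercurrent illness are left out.
- **Hematologic group.** It opens "For Hematologic Toxicities, a DLT is defined as follows" and lists specific thresholds.
- **Hepatic group.** It opens with the same form of words, "For Hepatic Organ Toxicities, a DLT is defined as follows", and has five bullets: Grade 4 AST/ALT; AST/ALT above 3 × ULN with Grade ≥2 bilirubin and ALP below 2 × ULN; and three AST/ALT limits (5, 5 and 8 × ULN) set by liver metastases and baseline level. Bilirubin appears only in the second, the Hy's law bullet ("blood total bilirubin increased with serum alkaline phosphatase").
- **Remaining group.** Only this heading repeats the general rule: "Non-Hepatic Major Organ Toxicities, a DLT is defined as all TEAEs of Grade" ≥3, with exceptions. The catch-all line, and the clause sending events to joint discussion by the Investigator, Medical Monitor and Sponsor, both belong to this group.

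Table 2 in Section 6 gives bilirubin its own rows. Grade 3 means a delay and then either a one-level reduction or, if resolution takes more than 7 days, "days from day of onset, discontinue DS-6157a". For Grade 4 the action is "Discontinue patient from study treatment".

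**The concern.** Two people applying Section 5.1.2 to the same patient could reach different answers. One would start from the general rule and find no exception for bilirubin. The other would go to the hepatic definition, find no bullet that fits, and record no DLT. Both have wording to point to.

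This matters because the BLRM takes one binary outcome per evaluable patient. Section 1.2 names hepatotoxicity as an important potential risk and says the escalation data are being analysed to choose a dose. Under the second approach, a Cycle 1 bilirubin event serious enough for Table 2 to stop treatment would reach the model as a tolerated dose. The same input also feeds the MTD estimate in Section 5.1.3.

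**Working it through.** **Step 1. Which bilirubin events meet no hepatic bullet?** Take Grade ≥3 bilirubin in Cycle 1.

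- AST/ALT ≤3 × ULN: no bullet is met, whatever the ALP.
- AST/ALT >3 × ULN and ALP <2 × ULN: the Hy's law bullet is met, so it is a DLT.
- AST/ALT >3 × ULN, ALP ≥2 × ULN, and AST/ALT within the applicable limit (5 × ULN, or 8 × ULN with liver metastases and baseline above 3 × ULN): no bullet is met.

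The first and third cases are the gap.

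**Step 2. Does silence in a list override the general rule?**

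- *Evidence that it does.* The hematologic list uses the same opening and omits Grade 3 neutropenia, and Grade 4 neutropenia of 7 days or less, without calling either an exception. If the general rule survived that silence, the more-than-7-days condition would do nothing.
- *Evidence that it does not.* No text excepts bilirubin. The hematologic thresholds each replace the default for an analyte they name; no hepatic bullet sets a threshold for bilirubin alone. The Hy's law bullet widens capture, reaching down to Grade 2.

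The second set is stronger, so the general rule is the better reading. The text does not state it.

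**Step 3. What would one uncounted event do to the model?**

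Inputs, from Sections 10.7.1 to 10.7.4:

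- logit π(d) = ln α + β ln(d/9.6)
- ln α ~ N(−1.125, 1.373²) and ln β ~ N(−0.308, 0.778²), correlation 0
- binomial likelihood for the DLT counts
- among doses with P(π > 0.33) < 25% and no more than double the current dose, choose the one with the highest P(0.16 < π ≤ 0.33)

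The posterior was computed by grid integration.

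*Reproducing the plan first.* With no data, P(π > 0.33) at 1.6, 3.2, 4.8, 6.4, 8.0 and 9.6 mg/kg is 11.7, 17.6, 23.0, 28.3, 33.3 and 38.1%. Appendix G Table 2.2, which is simulated, gives 12.3, 17.1, 23.5, 28.2, 31.7 and 37.6%. The largest gap is 33.3 − 31.7 = 1.6 points. The next-dose recommendations also match Appendix G Table 3.1 for all six rows used below.

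*First cohort, three patients at 1.6 mg/kg.* The increment limit is 2 × 1.6 = 3.2 mg/kg.

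| Outcome | Dose | P(target) | P(>33%) | Admissible? |
|---|---|---|---|---|
| 0/3 (event not counted) | 1.6 | 10.1% | 2.4% | yes |
| | 3.2 | 16.9% | 5.7% | yes, chosen |
| 1/3 (event counted) | 1.6 | 32.9% | 21.3% | yes, chosen |
| | 3.2 | 35.2% | 34.4% | no (≥25%) |

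These are rows 1.1 and 2.1 of Table 3.1 (3.2 and 1.6 mg/kg).

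*Two later cohorts, each with no DLT at the lower doses.*

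| Last cohort | Next dose, not counted | Next dose, counted | P(>33%) at the higher dose, counted |
|---|---|---|---|
| 3.2 mg/kg (rows 1.2, 1.13) | 6.4 | 4.8 | 29.7% |
| 6.4 mg/kg (rows 1.3, 1.4) | 9.6 | 8.0 | 29.0% |

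In each case the higher dose breaches the 25% cap once the event is counted.

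**The case against.** The strongest reply is that the section already has an answer. The general rule controls, bilirubin is not excepted, and the drafters wrote exceptions where they wanted them: Grade 3 lymphocyte decrease is expressly excluded, and ALP is named under "Grade 3 isolated laboratory findings not associated with signs or symptoms including alkaline phosphatase". This stands as the better reading. It does not remove the need for a sentence, because the hematologic list departs from the general rule without any express exception.

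A second reply is that Step 3 says nothing particular to bilirubin: leaving any DLT out of a three-patient cohort lowers the model's toxicity estimate. That is correct. The figures show what one misclassified event can do, not how likely one is.

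A third reply is that people, not the model, choose the dose. Section 5.1.1 requires clinical assessment of overall safety data, Appendix G says selection does not rest on the model alone, Section 5.1.3 weighs later-cycle safety, and Section 10.9 provides signal review at least monthly. A Grade 3 or 4 bilirubin would be seen. This limits the harm considerably, but it does not correct the model's input.

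A reader might also infer that bilirubin follows ALP, so that isolated asymptomatic Grade 3 is excepted. The documents do not support that: the exception sits under the non-hepatic heading and does not name bilirubin. Nor must DLT status mirror Table 2; the two serve different purposes.

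**Conclusion.** The point holds as an unclear classification rule that should be settled. Grade ≥3 bilirubin without a qualifying AST/ALT rise is best read as a DLT under the general rule, but the hepatic list is worded as a full definition and omits it.

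A reader might conclude that the protocol excludes these events from the DLT count, or that escalation has been unsafe. Neither follows. No text excludes them, and the documents do not show that any such event occurred or was left out.

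The consequence depends on two conditions: the hepatic list is applied as exhaustive, and at least one such event occurs in Cycle 1. Given both, one event can move the recommendation up a step, for example to 3.2 instead of 1.6 mg/kg after the first cohort, where the overdose probability with the event counted is 34.4% against the 25% cap. The documents give no event frequency, so no chance of this is claimed.

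**What to change.** Do one of the following in Section 5.1.2:

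- add a hepatic bullet: Grade ≥3 blood total bilirubin increased (CTCAE v5.0); or
- state that the general Grade ≥3 rule governs hepatic events not listed.

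Then confirm that any Grade ≥3 bilirubin in Cycle 1 of Part 1 was entered in the BLRM as a DLT. If one was not, correct it, re-run the model and document the change, since it would be made after the data were seen.

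A relaxation for Gilbert's syndrome or liver metastases is not part of this fix. Exempting Grade 3 events that resolve within 7 days in those patients would loosen the general rule for events where Table 2 still requires a one-level reduction. If the sponsor wants it, that is a clinical judgment to be stated openly.

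The cost is a one-line amendment and a check of Part 1 Cycle 1 bilirubin values, with possibly a slightly higher DLT count. No other DLT rule changes.
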